 - ii. In addition to surveys, the clinic staff will be trained to observe which patients talk with whom, as well as, the frequency and approximate duration of the conversation. The staff will be instructed to continue to assign seating based on clinical necessity and patient preference. Research staff, while they are performing the surveys or the COACH intervention, will also make and record observed patient interactions. Furthermore seating assignments

will also be collected. This data will be coded, patients will be de-identified for the analysis.

- iii. COACH is a behavioral communication intervention designed specifically for ESRD patients pursuing kidney transplantation. The COACH program (appendix) consists of four modules: 1) Kidney transplant options, 2) Discussing your transplant options, 3) Requesting living donation, and 4) Maintaining positive relationships. The content and teaching strategies were guided by the concepts of social cognitive theory as well as principles of adult learning and communication skills²²⁻²⁵. Another study coordinator will conduct the intervention in four, face to face, one hour sessions in the HD clinic. Patients will receive the accompanying handbook and video for the COACH intervention.
- iv. Using the data collected from the original survey and social network analysis, we will randomly select one transplant eligible patient (based on network attribute (most-clustered or most-central) per shift to participate in the COACH intervention.

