Analysis: We will compare and contrast both network and nodal attributes based on sex and race/ethnicity. We will use a multivariable linear regression to test if gender and race can predict clustering coefficient while controlling for age, HD vintage and socioeconomic status. We will refine our network model by adding and removing links with each wave of the survey. For the nodal attributes that are continuous variables, standard tests of hypothesis such as t-test, ANOVA, and linear regression will be used. For categorical attributes, ANOVA density-models as well as logistic regression models will be used. For continuous variables, testing distances and similarities, Moran statistics will be calculated. Since the observations are not independent observations drawn at random from a large population, we will use a boot-strap approach for estimating the variation of estimates from a large number of random sub-samples of network members⁵⁰⁻⁵².

Limitations: Having patients self-report their own social links, while an established methodology, can still be subject to recall bias⁵¹. Thus, we will use observations of social interactions for verification using the aforementioned log. These observations will be used to weight the survey generated links.

Approach to AIM 2: Using network information from AIM 1, we will examine how structural differences in social networks affect knowledge, attitudes, and behaviors towards kidney transplantation. **H2:** Patients with dense HD social networks have similar attitudes (both positive and negative) about transplantation and completion of steps to kidney transplant as compared to patients diffuse networks.

Rationale: We have found the primary barrier to the transplant wait-list is the completion of the work-up^{1,4}. Previous research shows that patients in small dense networks share similar ideas⁴². This could either positively^{1,26} or negatively¹⁰ affect access and progress to kidney transplantation. We are using steps completed to measure progress to transplantation; a measure has been established for transplant disparity research to improve the granularity of the measurement and compare results across studies².

Step	Description
1	suitability for referral to transplant center
2	interest in transplantation
3	referral call to transplant center
4	first visit to transplant center
5	transplant center work-up
6	work-up complete
7	active on the list
8	successfully received a kidney transplant

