Exposure: While only two patients per shift will receive the COACH intervention, all patients regardless of participation in the COACH education will be analyzed as exposed to the intervention via social spread. This will result in two groups for the primary analysis Cluster (MWF1 Cluster + TTS2 Cluster) and Central (MWF2 Central + TTS1 Central)

Analysis: To measure global changes, we will use a t-test to test changes in knowledge and changes in completion of steps between Cluster and Central. Individual level transfer of information will be analyzed with a

Markov chain Monte Carlo accept-reject procedure in the chain⁵⁸. We will examine the correlation in changes of a patient's(ego) knowledge with his or her first degree alter and measure the decay in correlation as the degree of the alter increases. We will also examine the ego's distance (how many links the patients are from each other) from the alter receiving the intervention. In addition, we will use Gaussian Conditional Random Fields (GCRF) methods to model a patient's stage in the transplant process by taking into account various factors such as personal demographics, social influence of alters, and global trends of HD shift and clinic⁵⁹. We will examine the characteristics of the patients disseminate and receive information. The data directly measuring the spread of information, influence, and behavior within the network from this experiment will be used to validate and strengthen the social network model developed in AIM1 and AIM2.

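### COACH sessions add observation time around the trained patients only, and the plan weights network links by observations without correcting for time observed

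*Protocol*

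**What the plan says.** Two groups of observers record who talks to whom. Protocol 7.d.ii first gives the task to clinic staff: "the clinic staff will be trained to observe which patients talk with whom, as well as, the frequency and approximate duration of the conversation". It then adds a second source: "Research staff, while they are performing the surveys or the COACH intervention, will also make and record observed patient interactions".

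Protocol 7.d.iii has a coordinator "conduct the intervention in four, face to face, one hour sessions in the HD clinic". The number of patients trained differs between the documents. Protocol 7.d.iv says "we will randomly select one transplant eligible patient" per shift. SAP AIM 3, Exposure, says "While only two patients per shift will receive the COACH intervention", in line with SAP AIM 3, Recruitment Goals.

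On use, SAP Analytic Plan AIM 1 names clinical observations, beside patient and staff surveys, as inputs to the network graphs. SAP AIM 1, Limitations, gives their purpose: "Thus, we will use observations of social interactions for verification using the aforementioned log". It continues: "These observations will be used to weight the survey generated links". SAP AIM 1, Analysis, revises links at every survey wave. According to SAP AIM 3, Analysis, Aim 3 data on spread "will be used to validate and strengthen the social network model developed in AIM1 and AIM2".

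**The concern.** A log of the frequency and duration of conversations depends on how long someone was there to see them. Before COACH, research staff log only while surveying, which involves every participant. From COACH on, they also log during sessions held with a few chosen patients. Ascertainment of ties can then change with treatment, both before versus after COACH and trained versus untrained, even if nobody's behaviour changes.

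At stake are the analyses that use ties near a trained patient: the correlation of change between a patient and his or her alters, the social-influence part of the Gaussian Conditional Random Fields (GCRF) model, and the return of Aim 3 results to the Aim 1 and 2 network model. The SAP Timeline also runs Aim 2 follow-up through Year 3, when the Aim 3 experiment is under way, so COACH-period entries could reach Aim 2 directly. If the weights partly reflect observer presence, estimates of spread from trained patients are distorted.

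**Working it through.** The plan states no figure for this, so there is none to reproduce. The check counts observer-hours.

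**Inputs from the documents**
- COACH: 4 sessions × 1 h = 4 h per trained patient (Protocol 7.d.iii; SAP Education Intervention).
- Shifts: 6 per clinic × 2 clinics = 12 (SAP Setting; SAP Sample size).
- Trained per shift: 2 (SAP) or 1 (Protocol).
- Surveys of all patients after COACH: 2, at 3 months and at one year (Protocol 7.d.v; SAP Staggered Surveys).
- Expected participants: 252, so 252/12 = 21 per shift (SAP Recruitment Goals).
- Chair time: 3 sessions a week × 4 h = 12 h a week (SAP Significance; the shift times in the AIM 3 assignment table).

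**Assumptions, not in the documents**
- Research-staff time per survey, s: 0.5 to 1 h.
- Share of chair time that clinic staff log, f: 1% to 100%.
- Window, W: 13 or 52 weeks.

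**Step 1. Hours added by COACH**
- Two targets: 2 × 4 = 8 h per shift; 8 × 12 = 96 h in total.
- One target: 1 × 4 = 4 h per shift; 4 × 12 = 48 h in total.

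**Step 2. Research staff alone, from COACH on.** Ratio = (4 + 2s) / 2s.
- s = 0.5: 5 h against 1 h, ratio 5.0.
- s = 1: 6 h against 2 h, ratio 3.0.

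With two targets, trained patients are 2/21 = 9.5% of participants. Their share of research-staff hours is 10/(21 + 8) = 34% at s = 0.5 and 12/(42 + 8) = 24% at s = 1.

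**Step 3. Adding the clinic-staff log, s = 0.5.** Ratio = (12fW + 1 + 4) / (12fW + 1).

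| f | W = 13 weeks | W = 52 weeks |
|---|---|---|
| 1% | 6.56/2.56 = 2.56 | 11.24/7.24 = 1.55 |
| 10% | 20.6/16.6 = 1.24 | 67.4/63.4 = 1.06 |
| 100% | 161/157 = 1.03 | 629/625 = 1.01 |

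The 13-week column keeps both surveys in the count as a simplification. With only the 3-month survey, the 1% entry would be 6.06/2.06 = 2.94.

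**Step 4. Which analyses can be reached**
- Target selection uses data collected in Aims 1 and 2, before COACH: not affected.
- The t-test of Cluster against Central on knowledge and steps uses no tie weights, and both arms train the same number per shift: not affected.
- Ego-alter correlation, GCRF social influence, the feedback to the Aim 1 and 2 model, and overlapping Aim 2 follow-up: exposed if the weights or links include COACH-session entries.
- Distance from the trained patient is a count of links, so it is exposed only if log entries add or remove links.

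**The case against.** The strongest reply is that clinic staff are the routine observers, with no restriction to trained patients, and research staff also log while surveying everyone. A reader might infer that observation as a whole is concentrated around trained patients. Step 3 shows that this depends on clinic-staff coverage, which the documents do not state. This objection stands.

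A reader might also infer that trained patients' ties must look stronger. The documents do not support that. Links originate in surveys, no weighting formula is given, and SAP Significance defines clustering and betweenness by counting. A patient in a one-hour face-to-face session may also talk less to neighbours, which would push the other way. So the direction is open. That does not remove the problem, because measurement would still differ by treatment.

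A third reply is that the SAP describes the log under Aim 1 and 2 data collection and does not list it for Aim 3, so entry of COACH-session records into the weights is an inference. That is fair. But the Protocol orders them recorded, Aim 2 follow-up runs alongside COACH, observations are named as graph inputs, and nothing excludes these entries. Likewise, the SAP does not say that GCRF uses log weights, and its feedback statement concerns data on spread rather than the log itself.

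Finally, no planned analysis compares tie strength before and after COACH, so a false claim that COACH activated the network is not a planned output. That also stands.

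**Conclusion.** The concern holds in limited form. As written, the plan lets ascertainment of ties vary with treatment, and it has neither a correction for time observed nor an exclusion of COACH-session entries. The possible consequence is bias of uncertain direction in trained patients' tie weights, confined to the diffusion analyses and the overlapping part of Aim 2.

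Only the added hours are firm: 4 per trained patient, and 48 or 96 in total according to which document is followed. The ratios rest on assumed survey length, clinic-staff coverage and window, and run from negligible to several-fold. A reader who counts one post-COACH survey would get 4.5/0.5 = 9 or 5/1 = 5 for research staff, but the plan has two surveys, which gives 5 or 3. Nothing here questions the choice of targets or the Cluster-versus-Central comparison. The point still merits a change because the source of an entry cannot be recovered later if it was not recorded.

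**What to change.** In Protocol 7.d.ii and SAP AIM 1:
- Flag the source of each log entry as clinic staff, survey session or COACH session.
- State that COACH-session entries are kept as a descriptive record and are not used to construct or weight links.
- Add a sensitivity analysis of the diffusion models using survey-only or pre-COACH links.
- Weighting per observed hour is optional, where hours are recorded. For the clinic-staff log this needs extra recording on every shift.

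Separately, the Protocol's one target per shift and the SAP's two must be reconciled, since this sets the observation load.

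The cost is a sentence or two in each document, one field on the log and some extra model runs. The downside is the loss from the network model of 48 to 96 hours of selectively located observations.

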- v. We propose a pre-post design to assess the impact of the COACH education on patients' transplant-related knowledge and behaviors. Before administering the COACH education, we will survey targeted patients to assess changes in knowledge and behaviors towards transplant from the baseline survey. As another measure of the impact of the COACH intervention, patients not receiving the intervention will serve as controls and will be surveyed along with those receiving the intervention; we will then assess within and between group differences in transplant-related knowledge and behaviors. To assess the dissemination of information contained in the COACH intervention, all patients will be surveyed at 3-months post-intervention. The follow-up surveys will determine the sources of these changes (eg. self-reading after the survey, the COACH intervention, or discussing with other patients). Finally, during Year 4, one year post-intervention, a final survey will be administered to all the patients in both clinics to assess retention of information and change in attitudes and behaviors of those who participated in COACH and the spread of information and behaviors to the patients who were not targeted.
- vi. The medical information collected is age, insurance status, ESRD diagnosis, vascular access. Medical comorbidities: congestive heart failure, peripheral vascular disease, malignancy. Mental Health, Substance Abuse, and HIV information is not collected. If the patient has ESRD from HIV the diagnosis is coded as glomerulonephritis a common and non-specific cause of ESRD.

Phosphate binding medication, Vitamin-D, and Calcimetic prescribing information is collected. Laboratory data includes basic metabolic panel, phosphorus, cbc, iron studies, hepatic function, cholesterol. Data collected will be analyzed to better understand barriers to transplantation and compare self-reported (survey) health data to laboratory data. All data is entered in an Excel spreadsheet and analyzed in SPSS 17.0, using descriptive statistics, chi-square test of association and t-tests. Time series analysis will be done in MathWorks MATLAB software. A p-value of less than 0.05 will be deemed significant.

- e. **Withdrawal of Subjects:** Patients may withdraw at anytime, this will be as a result of the patient transferring out of the clinic. Once, the patient withdraws they can contact the survey researcher or the PI and data will stop being collected.

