Transplant Eligibility: Previous studies have shown that not all suitable candidates are referred by their nephrologist. All patients will be evaluated via chart review by a study transplant nephrologist for transplant candidacy and, if eligible, the primary nephrologist will be asked whether the patient is an appropriate candidate and reasons they have not been referred. We will defer the transplant referral to the attending nephrologist. Our criteria for transplant ineligibility are nursing home resident, >79 years of age⁴⁷, active or recent malignancy, inoperable coronary artery disease, or comorbid illness that will make it unlikely that the patient will survive >3 years after transplant.

Recruitment Goals and Expected Survey Response (AIM 1 and AIM 2): Our goal will be to conduct a census. Our previous response rates^{1,4} have been consistently over 90%, most likely due to the non-invasive nature of the study. We anticipate recruiting 252 patients; however, we are budgeted as if all 280 patients participate.

Retention/Attrition: Based on our previous study¹, patients are amenable to repeated surveys and do not leave the HD clinic unless they transfer, are transplanted, or die. The mortality of transplant candidates is lower than the average mortality, and we are powered for an overall 2 year mortality¹⁸ of 10% and 5% transfer rate.

Participant Remuneration: Patients will receive a \$10 gift card after completing each survey.

Data Collection AIM1 and AIM2:

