patient selected by clustering, will have a clustering coefficient greater than 1 SD from the mean and centrality 1 SD less than a mean. In our previous study, there was no correlation between clustering and centrality ($r=0.024$, $p=0.875$). The research and clinical staff will be blinded to whether the patient was chosen to participate in COACH because of clustering or centrality. Patients will be excluded if they are ineligible for a kidney transplant, had a previous kidney transplant, or have an active living donor.

Assignment of Intervention groups: The intervention assignment will be alternated between MWF and TTS (Table 3) to avoid patient differences between those respective days (for example patients on MWF may have been on dialysis longer while patients on TTS may be more likely to work)⁵⁵.

Retention/Attrition: **AIM3** will be carried out over the course of a year with a possible drop-out rate of 5% (Death and Transfer). If a patient transfers, the patient will be contacted via phone to do a follow-up survey.

Participant Remuneration: All patients will receive \$10 for the initial survey (Wave 1), and Wave 2 survey, \$10 for the 3 month follow-up (Wave 3), and \$10 for Wave 4. Patients will not receive remuneration for participating in the COACH education but will be able to keep the handouts and reading materials.

Data Collection (AIM 3)

Education Intervention: COACH is a behavioral communication intervention designed specifically for ESRD patients pursuing kidney transplantation. The COACH program (appendix) consists of four modules: 1) Kidney transplant options, 2) Discussing your transplant options, 3) Requesting living donation, and 4) Maintaining positive relationships. The content and teaching strategies were guided by the concepts of social cognitive theory as well as principles of adult learning and communication skill acquisition^{31,56,57}. A study coordinator will conduct the intervention in four, face to face, one hour sessions in the HD clinic. Patients will receive the a handbook and video for the COACH intervention.

Shift	Clinic 1		Clinic 2	
	MWF1	TTS1	MWF2	TTS2
1st 5am-9am	Cluster	Central	Central	Cluster
2nd 9am-1pm	Cluster	Central	Central	Cluster
3rd 1pm-5pm	Cluster	Central	Central	Cluster

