Staggered Surveys: We propose a pre-post design to assess the impact of the COACH education on patients' transplant-related knowledge and behaviors. Before administering the COACH education, we will survey targeted patients to assess changes in knowledge and behaviors towards transplant from the baseline survey. As another measure of the impact of the COACH intervention, patients not receiving the intervention will serve as controls and will be surveyed along with those receiving the intervention; we will then assess within and between group differences in transplant-related knowledge and behaviors. To assess the dissemination of information contained in the COACH intervention, all patients will be surveyed at 3-months post-intervention. The follow-up surveys will determine the sources of these changes (eg. self-reading after the survey, the COACH intervention, or discussing with other patients). Finally, during Year 4, one year post-intervention, a final survey will be administered to the all the patients in both clinics to assess retention of information and change in attitudes and behaviors of those who participated in COACH and the spread of information and behaviors to the patients who were not targeted.

Clinical Data: In addition to the survey data, we will collect patient transplant listing status, living donor evaluations from participants' respective transplant centers.

Analytic plan AIM3: To test **H3** we will assess the successful spread of the intervention by evaluating the difference in the primary outcome of completion of steps toward transplantation between patients being exposed via the most clustered (Cluster) members versus the most central (Central). We will use repeated surveys to measure our secondary outcomes include change in knowledge, attitudes, behaviors of the patients either directly exposed to the intervention or those who were exposed indirectly through the social network.

Primary Outcomes: 1) Differences in patient knowledge, 2) Differences in transplant steps completed

Secondary Outcomes: 1) Completion of transplant work-up, 2) Asking for a living donor

Independent Variables: Intervention assignment to Cluster or Central

Covariates: Age, Marital Status, insurance, transplant eligibility, HD shift, HD Clinic, network attributes

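### Protocol and SAP give conflicting rules for transferred patients, and neither states how transplanted patients are surveyed, so AIM 3 knowledge data may be missing in a way related to outcome

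*Protocol*

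**What the plan says.** **Transfer.** Protocol 7.e (Withdrawal of Subjects) states: "Patients may withdraw at anytime, this will be as a result of the patient transferring out of the clinic". It continues: "Once, the patient withdraws they can contact the survey researcher or the PI and data will stop being collected". The SAP, under AIM 3 Retention/Attrition, states: "If a patient transfers, the patient will be contacted via phone to do a follow-up survey".

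**Transplant.** The SAP's Retention/Attrition paragraph for AIMs 1 and 2 says that patients "do not leave the HD clinic unless they transfer, are transplanted, or die". Its allowance there is a two-year mortality "of 10% and 5% transfer rate". For AIM 3 the SAP gives a "possible drop-out rate of 5% (Death and Transfer"). Neither allowance includes transplant, and the phone survey names only patients who transfer.

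**Wave 4.** Both documents describe the last survey in nearly the same words. In the SAP (Staggered Surveys), "a final survey will be administered to the all the patients in both clinics"; in Protocol 7.d.v, "a final survey will be administered to all the patients in both clinics".

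**Outcomes and their sources.** The AIM 3 analytic plan lists differences in knowledge and in steps completed as primary outcomes. Knowledge is a score from 12 true/false items in the patient questionnaire (SAP, Survey Instrument). Receiving a transplant is step 8, the top of the step scale (SAP, Approach to AIM 2). Steps are recorded as clinical data and listing status is verified with the transplant centre (SAP, Clinical Data for AIMs 1 and 2; AIM 2 Limitations). For AIM 3, listing status and donor evaluations are also collected from the centres.

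**The concern.** The two transfer rules cannot both be followed. Under the Protocol a transferred patient may be treated as withdrawn, with no further data. Under the SAP the same patient is phoned and contributes a survey.

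For transplanted patients there is a gap rather than a conflict. The plan recognises that they leave the clinic, but states no way of surveying them afterwards. A site could reasonably take the Wave 4 wording to mean those still dialysing there. A patient transplanted before Wave 3 or 4 would then have no knowledge, attitude or donor answers at that wave.

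That missingness is related to outcome. The patients concerned are by definition at the top of the step scale, which is the other primary outcome, and they may well differ from the rest in knowledge and in having asked for a donor. A transplant centre's record cannot supply a questionnaire score. The plan gives no rule for missing surveys. Its one reference to intention to treat concerns a shift on which nobody takes COACH (SAP, AIM 3 Limitations).

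**Working it through.** **1. Who is covered by what.**

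| Way of leaving (SAP) | Protocol 7.e | AIM 3 drop-out figure | SAP phone survey | Step outcome | Knowledge score |
|---|---|---|---|---|---|
| Transfer | withdrawal, data stop | counted | yes | clinical data, centre status | depends on which rule is applied |
| Transplant | not mentioned | not counted | not mentioned | step 8, status from centre | no stated route |
| Death | not mentioned | counted | not applicable | up to death | up to death |

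**2. The SAP's own power figures.** I used a two-sample t-test, two-sided alpha 0.05, noncentral t, without adjustment for shift, as in the SAP.
- Steps, effect size 1.06: n = 14.99, so 15 per arm, power 80.0%. This reproduces the stated total of 30.
- Steps, 1 step, effect size 1.06/2 = 0.53: 60 per arm gives 82.1%.
- Knowledge, half of 1.2 = 0.6: 45 per arm gives 80.4%.

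**3. Reserve for further loss of knowledge scores.** These figures treat the loss as random, so they show precision only.
- From 45 per arm: 5% loss leaves 45 × 0.95 = 42.75, about 43, power 78.5%. At 40 per arm it is 75.5%; at 36 it is 70.9%.
- If all 60 per arm supply a score: 90.3%. At 57 (5% loss) it is 88.8%; at 51 (15% loss) it is 85.1%.

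The reserve depends on which sample supplies the knowledge score. At the SAP's figure of 45 per arm there is almost none.

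**4. Bias in knowledge.** In one arm let p be the proportion transplanted before the survey, T their mean score and R the mean of the rest. The full mean is (1 − p)R + pT, so analysing only the rest shifts the arm mean by R − [(1 − p)R + pT] = −p(T − R). The Cluster minus Central difference shifts by −p_Cluster(T − R)_Cluster + p_Central(T − R)_Central. The documents give none of these four quantities, so neither sign nor size can be computed.

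**5. Would the direction be clear even for steps?** Suppose, against the plan's intent, that step-8 patients were also dropped from the step analysis. With full mean M, the rest have mean (M − 8p)/(1 − p). The proportions below are assumptions.

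| Full means | Step 8, Cluster / Central | Means of the rest | Difference |
|---|---|---|---|
| 6 v 5 | 5% / 5% | 5.89 v 4.84 | 1.05 (full 1.00) |
| 6 v 5 | 10% / 5% | 5.78 v 4.84 | 0.94 (full 1.00) |
| 6 v 5 | 20% / 5% | 5.50 v 4.84 | 0.66 (full 1.00) |
| 7 v 5 | 10% / 5% | 6.89 v 4.84 | 2.05 (full 2.00) |

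The last row uses only the SAP's planning means. Taken with its SDs (7, SD 1.5 v 5, SD 1.7) on whole steps 1 to 8, those values require at least 32% of Cluster patients at step 8 and allow 0% to 24% in Central. For Cluster, let Y = 8 − step: mean 1, mean square 1 + 1.5² = 3.25. For whole Y from 1 to 7, (8Y − Y²)/7 is at least 1, so the share with Y ≥ 1 is at most (8 − 3.25)/7 = 0.68. With 32% in Cluster, the rest average (7 − 2.56)/0.68 = 6.53. Central is 5.00 at 0%, giving a difference of 1.53, or (5 − 1.92)/0.76 = 4.05 at 24%, giving 2.48. The full difference is 2.00, so the shift can go either way here too.

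**The case against.** The strongest reply is that the plan does not lose its successes. Transplant is itself step 8, steps are recorded as clinical data, and status is confirmed with the centres. No sentence removes transplanted patients from the AIM 3 analysis. This stands for the step outcome. It does not help the knowledge score, which exists only as questionnaire answers.

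Second, Protocol 7.e can be read more narrowly: the stop in data collection is worded around the patient contacting the study. That is fair, but the preceding sentence still presents transfer as the reason for withdrawal, and a site would have to guess.

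Third, the Wave 4 wording can mean all enrolled patients of both clinics. That reading is possible and probably intended, but no contact route is stated for those who have left by transplant.

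A reader might go further and infer any of the following, which the documents do not support:
- **That the Protocol stops data for transplanted patients.** Protocol 7.e names transfer only.
- **That AIM 3 loses its best outcomes on steps, or that the Cluster v Central difference is pulled toward zero.** Step 8 should be recoverable, and the direction is not fixed (working, item 5). The earlier study's denser networks in transplanted patients (0.71 v 0.23) describe a patient's own clustering, whereas the AIM 3 exposure is a targeting strategy assigned by shift.
- **That transplanted patients vanish as nodes.** The AIM 1 analysis adds and removes links at each wave. It does not say that nodes are deleted, and the AIM 2 model uses the alters' current step.

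**Conclusion.** The point holds in two parts. First, Protocol and SAP contradict each other on transferred patients and must be reconciled. Second, transplant is recognised as a way of leaving but is missing from the AIM 3 drop-out figure and from the phone follow-up. Knowledge, attitude and donor answers at Waves 3 and 4 therefore have no assured source for these patients, and their absence would be related to outcome.

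The size is limited and partly unknown. Transfers and transplants are a minority under most assumptions, but the documents give no transplant rate. The planning values taken at face value would put at least 32% of Cluster patients at step 8. They come from an earlier three-year study and may be rounded, so this is not a forecast; it does show that the group cannot be assumed negligible. The precision cost for knowledge is a fall from 80.4% to 78.5% at the SAP's own 5% loss from 45 per arm, and more if transplants add to it. It is milder if all 60 per arm supply a score. No claim about the direction or amount of bias is justified. The conclusion assumes that a site applies the text as written and adds no follow-up of its own. It should be corrected, but it does not undermine the step outcome.

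**What to change.** 1. Amend Protocol 7.e so that leaving the clinic by transfer or transplant is not withdrawal, and only the patient's own request stops data collection. Align it with the SAP's AIM 3 Retention/Attrition paragraph.
2. Extend the SAP's phone survey to transplanted patients at Waves 3 and 4, and define the Wave 4 population as all enrolled patients, wherever they are by then.
3. State in the AIM 3 analytic plan that transplanted patients remain in the analysis, scored at step 8 from transplant-centre records, and remain as alters at that step in the AIM 2 and AIM 3 models.
4. Add transplant to the AIM 3 attrition allowance, with the assumed rate stated, and say how missing knowledge scores will be handled.

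The cost is one protocol amendment, a few sentences in the SAP and a small number of calls on a route already planned. The downside is that phone answers may differ slightly from answers given in the clinic, so the mode of each survey should be recorded.
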